9.3 Planned Sample Size

In Part A, up to 70 healthy female volunteers aged 18 to 40 will be randomised (i.e. up to 7 cohorts of 10 volunteers).

In Part B, up to 240 healthy female volunteers aged 18 to 40 will be randomised (i.e. 3 cohorts of 80 volunteers). The final number of volunteers to be randomised in Part B will be calculated following a review of the data from Part A, and will not exceed 240 volunteers.

At least 7 evaluable volunteers in Part A are required to attend through visit 4 in each cohort in order to provide sufficient data for a decision to dose escalate. If the required number of evaluable volunteers are not obtained in a cohort, then replacement volunteers must be dosed for that cohort, prior to considering dose escalation.

9.4 Allocation of Randomisation Numbers

Each randomised volunteer will be allocated a four digit randomisation number. The randomisation numbers for Part A will be 1001 to 1070, and for Part B will be 2001 to 2240.

In Part A, replacement volunteers will be allocated a randomisation number which is equal to the randomisation number of the volunteer they are replacing plus 100, and they will

receive the same treatment as the volunteer they are replacing, e.g. if randomisation number 1003 is replaced, the replacement volunteer will be allocated the randomisation number 1103.

In Part B, replacement volunteers will be allocated a randomisation number which is equal to the randomisation number of the volunteer they are replacing plus 500, and they will receive the same treatment as the volunteer they are replacing, e.g. if randomisation number 2003 is replaced, the replacement volunteer will be allocated the randomisation number 2503.

9.5 Volunteer Withdrawal

The volunteer has the right to abstain from participation in the study or to withdraw consent to participate at any time without penalty. The Sponsor or the Investigator also holds the responsibility to withdraw a randomised volunteer from the study prematurely if it is considered in the best interest of the volunteer. The entire study may be stopped if there are unpredicted safety concerns.

A volunteer's participation may be discontinued at any point during the study without implications on further medical care if:

- They no longer wish to participate.
- The physician feels it is in their best interest to withdraw.
- The volunteer deviates from the treatment plan specified in the protocol (e.g. failure to attend study visits).
- The volunteer is no longer willing to comply with the requirements of the study protocol.
- The study is prematurely terminated, see Section 9.7.

If the participation of any volunteer ceases prematurely, the reasons leading to withdrawal from the study should be described in detail. A post-study medical should be performed as described in Section 12.2. The case report form (CRF) must be completed as fully as possible giving reasons for withdrawal when available.

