Visit 9 will be performed 8 weeks following the first study vaccine administration and the following assessments will be performed: an assessment of the injection site and a pharmacodynamic blood sample will be taken to measure antibody response and AEs and concomitant medications will be reviewed.

Post-Study Medical (Visit 10)

A post-study medical will be performed 12 weeks following the first study vaccine administration and the following assessments will be carried out: an assessment of the injection site, a pharmacodynamic blood sample will be taken to measure antibody response, physical examination, vital signs, 12-lead ECG, urinalysis, blood samples for haematology and biochemistry, serum pregnancy test (if applicable) and a review of AEs and concomitant medications.

Safety Follow-Up (Visit 11)

A safety follow-up phone call will be performed 3 months after the end of the study (Visit 10) i.e. 6 months following the first study vaccine administration to check the general health of the volunteer and to review significant AEs.

[REDACTED]

In both Part A and Part B, following the primary dose volunteers will remain in the study unit for 8 hours post-dose to ensure that no significant AEs occur and the medicinal product is well tolerated. No additional acute safety concerns are considered likely to occur following 8 hours of observation. Following the booster dose volunteers will remain

in the clinic for at least 4 hours post-dose, as the volunteer has tolerated the initial dose, and therefore, tolerability should be consistent. The concern is for an acute systemic reaction following the booster dose. It is not considered necessary to keep the volunteers in the study unit overnight as no samples are being taken and the time intervals are considered appropriate to assess the safety and tolerability prior to discharge.

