Visit 9 (week 8) and Visit 10 (week 12, timing of primary endpoint) will take place at the study unit and the following assessments will be performed: vaginal and rectal swabs will be taken to assess colonisation by GBS, a pharmacodynamic blood sample will be taken to measure antibody response, vital signs will be recorded, an assessment of the injection sites will be performed and AEs and concomitant medications will be reviewed. At Visit 10 (week 12) a urine pregnancy test will also be performed.

Visits 11, 12, 13, 14, 15, 16, 17, 18 and 19

Visit 11 (week 16), Visit 13 (week 24), Visit 15 (week 32) and Visit 17 (week 40) will take place at the study unit and the following assessments will be performed: vaginal and rectal swabs will be taken to assess colonisation by GBS, a pharmacodynamic blood sample will be taken to measure antibody response, vital signs will be recorded, an assessment of the injection site will be performed and significant AEs and concomitant medications will be reviewed.

The remaining visits [Visit 12 (week 20), Visit 14 (week 28), Visit 16 (week 36), Visit 18 (week 44) and Visit 19 (week 48)] will be conducted via a phone call and AE's and concomitant medications will be reviewed.

Post-Study Medical (Visit 20)

A post-study medical will be performed 12 months following the first injection and the following assessments will be carried out: an assessment of the injection site, vaginal and rectal swabs will be taken to assess colonisation, a pharmacodynamic blood sample will

be taken to measure antibody response, physical examination, vital signs (heart rate and blood pressure, including tympanic temperature and respiration rate), 12-lead electrocardiogram (ECG), urinalysis, blood samples for haematology and biochemistry, serum pregnancy test (if applicable) and a review of AEs and concomitant medications.

[REDACTED]

Phenotypic and genetic analyses may be performed on GBS strains isolated from volunteers' vaginal and rectal swabs.

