12.6 Individual Volunteer Stopping Criteria

Volunteers who meet one or more of the following stopping criteria will receive no further doses of study vaccine but will be followed up for safety:

- Severe injection site reaction, see Appendix 1
- Severe systemic reaction, e.g. anaphylaxis, see section 14.2.1
- Persistent febrile reaction (>38.9°C and >24 hours) at the Investigator's discretion
- SAE related to the study agent

The medical safety of the volunteer is of paramount importance when discussing study continuation.

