14. ADVERSE EVENTS, SERIOUS ADVERSE EVENTS AND REPORTING

14.1 Adverse Events (AEs)

An AE is any untoward medical occurrence in a volunteer to whom a medicinal product has been administered, including occurrences which are not necessarily caused by or related to that product.

An AE can be:

- Any unfavourable and unintended sign (including reactions from overdose, abuse, incorrect use of any treatment, or interaction)
- Any new disease or exacerbation of an existing disease (e.g. increase in frequency or worsening in nature)
- Any deterioration in measurements of laboratory values or other clinical tests (e.g. ECG, vital signs or X-ray) that results in symptoms, a change in treatment, or discontinuation from the IMP
- Recurrence of an intermittent medical condition (e.g. headache) not present at baseline
- Other medical events regardless of their relationship to the IMP, such as accidents, falls and any injuries resulting from them.

AEs will be recorded from the start of the study, i.e. from the first visit to the study unit on Day 1, until the post-study medical visit.

After completion of the 12 week period following the first vaccination in Part B (i.e. after Visit 10), AEs will be recorded by the volunteer in a diary card, and only those deemed to be relevant or significant by the Investigator will be recorded in the eCRF. A relevant or significant AE will be any event that caused the patient to visit any health care professional. These events will be recorded and the Investigator will determine if the event was possibly related to the investigational product. Any event deemed serious will be processed as a SAE in the normal way and if considered related reported as a SUSAR.

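### A vaccinated woman can be taken out of the study for missed visits without withdrawing consent; no scheduled adverse-event contact is then set, yet she stays in the ITT denominator

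*Combined protocol and SAP*

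**What the plan says.** Section 9.5 (Volunteer Withdrawal) says when participation may be discontinued. One ground is that the woman no longer wishes to take part. A separate ground is "The volunteer deviates from the treatment plan specified in the protocol (e.g. failure to attend study visits". When participation ends early, the section asks for detailed reasons, a CRF as complete as possible, and one assessment: "A post-study medical should be performed as described in Section 12.2".

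Section 12.2 gives that medical one date per part. For Part A (12.2.1): "A post-study medical will be performed 12 weeks following the first study vaccine administration". For Part B (12.2.2): "A post-study medical will be performed 12 months following the first injection". Neither says what happens on early exit. Part A also has a later call: "A safety follow-up phone call will be performed 3 months after the end of the study (Visit 10"). The text does not say whether a removed woman receives it.

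Section 12.6 covers women who meet a safety stopping criterion: a severe injection-site reaction, a severe systemic reaction, persistent fever, or a related SAE. They "will receive no further doses of study vaccine but will be followed up for safety". Missed visits are not on that list.

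Section 14.1 records AEs "from the first visit to the study unit on Day 1, until the post-study medical visit". In Part B after Visit 10, volunteers keep a diary card and "only those deemed to be relevant or significant by the Investigator will be recorded in the eCRF". Section 14.3 has volunteers report AEs spontaneously, and has reported AEs recorded, up to Day 85. Section 15.4.2 includes withdrawals and dropouts in the safety analysis and bases the TEAE percentage on ITT. Section 15.2 does not replace missing data.

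**The concern.** The protocol separates stopping vaccine from stopping follow-up in 12.6 but not in 9.5. A woman who has been dosed and has not withdrawn consent can therefore leave AE follow-up by a study decision. If a later event of hers goes unrecorded, she counts as having had no TEAE, because she remains in the denominator.

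Safety to Week 12 is the primary objective, safety to 1 year is the secondary safety objective of Part B, and the vaccine has not been given to humans before. The error runs one way, towards a safer-looking vaccine. Women may miss visits because they felt unwell after the first dose, so the loss need not be random. What is at risk is active questioning about new, mainly non-serious events. The by-visit summaries of laboratory values, vital signs and reactogenicity are not affected in this way.

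**Working it through.** The plan gives no removal rate and no AE rates, so it has no figure of its own to reproduce. The text is checked first; the size is then given per removed woman.

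**Two readings of the timing of the medical**

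- *At its Section 12.2 date.* Recording under 14.1 runs to Week 12 (Part A) or Week 52 (Part B), and most of the gap closes. A removed Part B woman still has no scheduled AE contact at Week 12, the end of the primary window; her next named AE review is at 12 months.
- *At exit.* Recording under 14.1 ends there, and nothing further is scheduled in either part. Three reactive duties remain: recording of events reported up to Day 85, with follow-up of ongoing related AEs and related SAEs (14.3), and reporting of any SAE that comes to the Investigator's attention during the study period (14.5.1).

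**Bound without a model**

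One woman misclassified as event-free lowers the percentage by at most 100/60 = 1.67 points (60 actives per Part B group, 12.2.2) or 100/8 = 12.5 points (8 actives per Part A cohort, 12.2.1).

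**Expected shift if the medical is done at exit**

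Assumptions, none of them from the documents: exit at week 4, no booster, no spontaneous reports, and a constant background hazard.

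- Rb: 12-week background AE risk, 30% or 10%; weekly hazard h = −ln(1 − Rb)/12.
- p1: chance of a dose-1 reaction already recorded before exit, 0, 30 or 60%.
- Q: risk in weeks 12 to 52 of an AE leading to a health-care visit (the post-Day-85 rule in 14.1), 30% or 10%.

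The chance that a removed woman is wrongly counted as having no TEAE is

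- 12 weeks: m12 = (1 − p1) · exp(−4h) · [1 − exp(−8h)]
- 1 year: m52 = (1 − p1) · exp(−4h) · [1 − exp(−8h) · (1 − Q)]

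The shift in points is 100·m/60 or 100·m/8. For Rb = 30%, exp(−4h) = 0.888 and exp(−8h) = 0.788. With p1 = 0, m12 = 0.888 × 0.212 = 0.188, and 18.8/60 = 0.31 points.

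| Points per removed woman | p1 = 0 | p1 = 30% | p1 = 60% |
|---|---|---|---|
| 12 weeks, of 60, Rb 30% | 0.31 | 0.22 | 0.13 |
| 12 weeks, of 60, Rb 10% | 0.11 | 0.08 | 0.04 |
| 12 weeks, of 8, Rb 30% | 2.3 | 1.6 | 0.9 |
| 1 year, of 60, Rb 30%, Q 30% | 0.66 | 0.46 | 0.27 |
| 1 year, of 60, Rb 30%, Q 10% | 0.43 | 0.30 | 0.17 |

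**Against sampling error** (n = 60, p1 = 30%, Rb = 30%)

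- 12 weeks: true risk 1 − 0.7 × 0.7 = 0.51; SE = √(0.51 × 0.49/60) = 6.45 points; 6.45/0.219 ≈ 29 women removed to shift the figure by one SE.
- 1 year, Q = 30%: risk 0.657, SE 6.13 points; 6.13/0.464 ≈ 13 women.
- 1 year, Q = 10%: risk 0.559, SE 6.41 points; 6.41/0.301 ≈ 21 women.
- Part A, n = 8, risk 30%: SE 16.2 points, against 2.3 points per removed woman (p1 = 0).

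**The case against.** The best defence is that the harm needs a reading the text does not state. Taken literally, the reference to Section 12.2 puts the medical, with its AE review, at the end of the primary window in Part A and of the secondary window in Part B. Section 14.3 also runs recording to Day 85 whenever the medical takes place, so setting spontaneous reports to zero gives upper-end shifts. A woman who felt unwell after dose 1 and had it recorded already has a TEAE and cannot be undercounted; the shifts fall as p1 rises. The rule is discretionary. Severe reactions and related SAEs stay in follow-up under 12.6, and blinding of site staff (10.4) limits removal that differs by arm. Section 6.3 says all volunteers are monitored throughout. Numbers leaving early will show in the disposition summary.

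Most of this stands, and it is why the point is minor. It does not remove the gap. The remaining provisions cover events she volunteers or the site already knows of; none sets a contact to ask about new ones. Section 6.3 refers back to the protocol and adds no schedule. Even the literal reading leaves a removed Part B woman without a Week 12 contact.

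**Conclusion.** The concern holds, as a minor one. The protocol permits a consenting, vaccinated woman to leave scheduled AE follow-up while she stays in the TEAE denominator, and it leaves the timing of her last assessment open.

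Any resulting error makes the cumulative TEAE percentage too low, more so at 1 year than at 12 weeks. It is modest and probably below one standard error: in the worked case about 29 of 60 women would have to be removed to reach that at 12 weeks, and 13 to 21 at 1 year. These sizes assume a medical at exit in week 4, no booster, no spontaneous reporting and the AE risks stated above. Spontaneous reporting would make them smaller. The actual total cannot be derived, because the documents give no removal rate.

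**What to change.** The main change is in Section 9.5: deviation or non-attendance may stop further dosing but, unless the woman withdraws consent, she stays in AE follow-up on the existing schedule, by telephone if she will not attend. In Part A this runs to Day 85 plus the Visit 11 call; in Part B, to Visit 20.

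Three small additions go with it:

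- In 9.5, state when the post-study medical is done on early exit.
- In 14.1, for women who stop early only, continue AE recording to the scheduled date of the medical (Day 85 in Part A; Day 365 in Part B, under the existing post-Day-85 rule).
- In 15.4.2, show the number still under AE follow-up at Day 85 and, for Part B, at Day 365 beside the cumulative TEAE percentages.

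The cost is two sentences in 9.5, one in 14.1, one count in the tables, and a few telephone reviews of the kind Part B already schedules. A protocol amendment also needs Ethics Committee approval (16.2), so the change is best made with the next amendment. No new procedures or volunteers are needed, and recording for women who complete is unchanged. Some women who miss visits will not answer calls, so the gain is partial.

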9.6 Volunteer Replacement

At least 7 evaluable volunteers in Part A are required to attend through visit 4 in each cohort in order to provide sufficient data for a decision to dose escalate. If the required number of evaluable volunteers are not obtained in a cohort, then replacement volunteers must be dosed for that cohort, prior to considering dose escalation.

9.7 Premature Termination of the Study

Following review by the Sponsor and the Investigator, the study may be terminated prematurely if:

- There are new toxicological or pharmacological findings, serious adverse events (AEs) or frequent severe AEs likely to be related to the vaccine that invalidate the positive benefit-risk assessment.
- AEs occur in such prominence (i.e. severity and frequency) that the proposed schedule can no longer be adhered to.

- Significant protocol deviations occur at a frequency implicating the valid and safe conduct of the study.
- The Sponsor decides to discontinue the study.

The individual stopping criteria and study stopping criteria are described in Sections 12.6 and 12.7.

10. INVESTIGATIONAL MEDICINAL PRODUCT

10.1 Identity and Doses of IMP

The GBS-NN vaccine will be supplied [REDACTED]

[REDACTED]

[REDACTED]

[REDACTED]

[REDACTED]

In Part A, GBS-NN will be administered with and without Alhydrogel® (see table below for anticipated dose regimens). Cohorts in Part B may also receive GBS-NN without Alhydrogel® depending on the dosing regimens chosen. The procedure for the assembly of the different dose levels for Part A of the study is described in detail in the Pharmacy Procedure “Assembly of GBS-NN and placebo doses”. This procedure will be followed and, if required, amended to allow the assembly of additional dose strengths if indicated in Part B.

[REDACTED]

Individual volunteer treatments will be dispensed by the [REDACTED] pharmacist and labelled in accordance with Annex 13 of “The Rules Governing Medical Products in European Community, volume 4 Good Manufacturing Practice for Medicinal Products”.

The placebo vaccine [REDACTED]

[REDACTED]

It is currently anticipated that the following dosing strategy will be employed, however this may be modified, see below.

Part A:

Three dose levels will be selected, with and without Alhydrogel®: A, B, and C (where A is the lowest dose and C is the highest dose). It is anticipated that these doses will be 10µg, 50µg and 250µg, although these may be modified following ongoing review of data by the Safety Review Committee. The dose increase between cohorts will not exceed a five-fold increase.

It is anticipated that each cohort will receive the following dose regimen as described in the table below.

Note that cohort 7 is an optional cohort, and will proceed if deemed necessary to test an additional dosing regimen at a dose level below 250 µg, which will be determined following an ongoing review of the data.

Cohort	Dose schedule	Dose level	Adjuvant
1	Day 1, 29	10µg (A)	None
2	Day 1, 29	50µg (B)	None
3	Day 1, 29	10µg (A)	Alhydrogel®
4	Day 1, 29	250µg (C)	None
5	Day 1, 29	50µg (B)	Alhydrogel®
6	Day 1, 29	250µg (C)	Alhydrogel®
7	TBD	TBD, not exceeding 250 µg	TBD

Anticipated dose regimens in Part A

The aim of the dose finding overall is to identify the minimum dose level which provides the maximum immune response in terms of seroconversion rate, level of specific IgG reached and shortest time to peak level, whilst maintaining an acceptable safety profile.

It is anticipated that the results from Part A will indicate whether the optimal dose level lies between 10µg and 50µg, or between 50µg and 250µg. The effect of Alhydrogel® on these parameters will guide the decision on whether to include it in one or more cohorts in Part B.

Part B:

The levels of GBS-NN specific IgG observed in Part A at Day 57, along with the safety profile, will be used to define a narrower range of dose levels to explore in Part B, where the group sizes are larger and the significance of any observed differences in immune responses will be measurable.

It is currently anticipated that three dose regimens will be selected for evaluation in Part B. At least two dose levels will be evaluated, which may be the same or different to those administered in Part A, but will not exceed the highest dose administered in Part A. It is anticipated that the regimens in Part B will comprise two doses of Alhydrogel® adjuvanted vaccine with the second being administered after a variable interval, not exceeding four weeks. It is, however, possible that a single dose of vaccine may be evaluated in Part B.

10.2 Randomisation

Volunteers will be randomised pre-dose on the morning of Day 1, once all eligibility criteria have been verified. A randomisation list will be held on site, which will be accessible only to unblinded study personnel.

10.3 IMP Administration

Administration will be by intramuscular injection, preferably into the non-dominant arm. The dominant arm may be used if it is not possible to administer into the non-dominant arm e.g. due to an ongoing injection site reaction, or tattoo.

10.4 Blinding

This is a double-blind study. The study vaccine will be prepared at the study site by an unblinded pharmacy team as detailed in a separate instruction manual. The Investigator will have access to emergency envelopes at all times. In case of an emergency or any finding that requires unblinding to determine the identification of the treatment administered for the appropriate management of a volunteer on the study, the Investigator may break the blinding code for an individual volunteer. If the blind is broken the Investigator will inform the Sponsor, within 24 hours of breaking the blind, that the blind has been broken (but not necessarily the outcome of the breaking of the blind), and record the date, time and reason for breaking the blind.

Following database soft lock after visit 10 at 12 weeks for both Part A and Part B, dedicated members of the Data Management and Statistical teams will be unblinded. Study volunteers and clinical staff at the study site will remain blinded until after completion of the final follow-up visit in Week 52.

For the analysis of IgG concentration data up to Day 57 in Part A, to enable dose selection for Part B, a separate statistician will be unblinded to perform the analysis.

